6.7 Follow-up Visits

6.7.1 Telephone Follow-up

Follow-up phone visits will be completed on Days 7, 14 and 30 (± 2 days). It is imperative that all visits be completed on a timely and regular fashion. Generally, the Follow-Up Form will be the only form completed during the phone calls, but at times depending on participant's report, there may be another form or two. The follow up period includes all the time previous to the day of the interview. Any incidents that happen the day of the visit would be captured in the next Follow Up Visit.

There will be a set day that each subsequent visit should be completed for each participant. The research personnel should call all participant's phone numbers at least one time per day in order to collect the data. If more than 3 business days have passed from the set day, the RA should alert the PI that this week's Follow-Up Form has not yet been completed. If the RA is not able to contact the participant, a Missed Visit Report Form should be completed instead and the PI should be alerted once again.

If a participant is unmasked at any point in time during the study, the PI will be alerted immediately. A Georgetown University employee in the Department of Family Medicine not associated with the study will follow up with this participant from this point on. This particular research personnel is not to discuss any information regarding this occurrence with any other personnel other than the PI.

6.7.2 Telephone Follow Up Script

In general, the Day 7, 14 and 30 (± 2 days) follow up will be administered over the phone, but may be completed in person. These phone visits are when the primary data will be collected. It is imperative that all visits be completed on a timely and regular fashion.

- 1) *Drink Bin Number:* Make sure the participant has the correct drink bin number as you are completing the Follow-Up Form.
 - a) Ask the participant the number on the drink bottles and this should be confirmed with the randomization form.
 - b) If this number is not consistent, the participant should be alerted not consume any more drinks until further notice and the project coordinator should be immediately alerted after completing this week's Follow-Up Form.
- 2) *Daily Assessment Diary:* Ask the participant to collect the Daily Assessment Diary for the phone conversation. A lot of the information that will be collected on the Follow-Up Form has been collected by the participant on their Daily Assessment Diary. If they have not been using the Daily Assessment Diary, please positively stress the importance of the Daily Assessment Diary.
- 3) Explain to participant that we are supposed to fill out this Follow-Up Form today and it should take about 5 minutes.
- 4) Administer Follow-Up Form.
 - When entering sick days, missing school or work, etc., this should be generally whole integers. However, it is possible that a participant missed only 2 hours to go to the doctor. All numbers under 4 hours should be counted at 0.5 days, and all those above rounded up to next integer.
 - The participant needs to decide if any activities were missed due to an illness. This is for all illnesses, even those that we are not collecting data about.
 - For some questions the RA may say, "Did you visit a doctor?" A doctor is defined as any medical personnel in this study. Therefore, the participant may say, "Never, but s/he saw a nurse practitioner." Please count this the same as seeing the doctor.
 - *Compliance:* Please let the participant know that we would like them to consume the interventions, diaries, and sample collections as per the schedule, but regardless, we appreciate their participation.
 - *Adverse Events:* If the participant believes any AE occurred, it is imperative that the RA immediately fill out an AE Form, and if there are any SAE, alert the PI and project coordinator immediately.
 - Confirm the date and time for the next visit or call.
 - At day 7, remind the participant to take a photo of the remaining antibiotics bottles.
 - At day 14, remind the participant to take a photo of the remaining yogurt bottle.

6.7.3 Completion/Final Evaluation

On the final follow-up at day 30, participants will provide the final sample and be queried for changes in baseline health and other adverse events.

7. SAFETY ASSESSMENTS

7.1 Specification of Safety Parameters

We will alert the participants of the common reactions to yogurt and by listing common reactions for them to monitor. We will also have close follow-up and 24-hour phone line accessibility there is a question of an allergic or idiosyncratic reaction.

Details of all adverse events reported by participants or observed by research personnel will be recorded in the adverse event report forms. All adverse events observed will be recorded separately and all will be reported to the IRB on IRB Adverse Event forms.

In order to prevent the occurrence of adverse events, we will be stringent in enforcing our exclusion criteria, paying particular attention to the potential for an allergic reaction to strawberry or yogurt on the part of the participant.

Any participants who develops evidence of allergy or hypersensitivity to any component of the investigational product will be withdrawn from the clinical study and receive no further doses of either drink. We will continue to follow these participants for safety for the remainder of the study.

7.2 Methods and Timing for Assessing, Recording, and Analyzing Safety Parameters

Unanticipated problems will be recorded in the data collection system throughout the study.

Details of all expected and unexpected adverse events reported by participants during follow-up calls, spontaneously, or observed by research personnel must be recorded in the adverse event report forms. Participants will be provided with a daily diary with a list of the most likely possible adverse events (see **Table 10**), where they can document expected and other unexpected events not already listed. All non-serious adverse events will be reported to the IRB during continuing review. All AEs regardless of severity level will be evaluated by the DSMB during scheduled meetings.

If a participant reports an AE/SAE that does not yet have a Date of Resolution (ongoing) and is continuous (no more than two days without interruption) across two follow-up periods, this AE/SAE will be considered one event. The total duration of the AE/SAE will be collected but only one AE/SAE report form will be completed for this particular event. If the symptoms resolved for more than two days before recurrence, these will be reported as separate events.

The study staff will record all reportable events with start dates occurring any time after informed consent is obtained until 7 (for non-serious AEs) or 30 days (for SAEs) after the last day of study participation. At each study visit, the study staff will inquire about the occurrence of AE/SAEs since the last visit. Events will be followed for outcome information until satisfactory resolution or stabilization. In the event of SAEs, all clinical and laboratory investigations considered necessary by the investigator will continue until values have returned to normal. The investigator will provide the IRB with copies of results of examinations and treatment carried out during the follow-up of SAEs. These reports will be provided to the FDA and the NCCIH Program Official.

7.3 Adverse Events and Serious Adverse Events

An **adverse event (AE)** is any untoward medical occurrence in a participant during participation in the clinical study or with use of the experimental agent being studied. An adverse finding can include a sign, symptom, abnormal assessment (laboratory test value, vital signs, electrocardiogram finding, etc.), or any combination of these regardless of relationship to participation in the study. This includes events not

present at the start of the study, or worsening in grade during the course of the study. An AE can be reported anytime after study enrollment; a participant is considered enrolled once the informed consent form is signed.

A serious adverse event (SAE) is one that meets one or more of the following criteria:

- Results in death
- Is life-threatening (places the participant at immediate risk of death from the event as it occurred)
- Results in inpatient hospitalization or prolongation of existing hospitalization
- Results in a persistent or significant disability or incapacity
- Results in a congenital anomaly or birth defect

An important medical event that may not result in death, be life threatening, or require hospitalization may be considered an SAE when, based upon appropriate medical judgment, the event may jeopardize the participant and may require medical or surgical intervention to prevent one of the outcomes listed in this definition.

Unanticipated Problems (UP): The Office for Human Research Protections (OHRP) considers unanticipated problems involving risks to participants or others to include, in general, any incident, experience, or outcome that meets **all** of the following criteria:

- Unexpected in terms of nature, severity, or frequency given (a) the research procedures that are described in the protocol related documents, such as the IRB-approved research protocol and informed consent document; and (b) the characteristics of the participant population being studied;
- Related or possibly related to participation in the research (“possibly related” means there is a reasonable possibility that the incident, experience, or outcome may have been caused by the procedures involved in the research); and
- Suggests that the research places participants or others at a greater risk of harm (including physical, psychological, economic, or social harm) than was previously known or recognized.

7.4 Characteristics of an Adverse Event

7.4.1 Relationship to Study Intervention

To assess relationship of an event to study intervention, the following guidelines are used:

1. Related (Possibly Related, Probably Related, Definitely Related)
 - a. The event is known to occur with the study intervention.
 - b. There is a temporal relationship between the intervention and event onset.
 - c. The event abates when the intervention is discontinued.
 - d. The event reappears upon a rechallenge with the intervention.
2. Not Related (Unlikely Related, Not Related)
 - a. There is no temporal relationship between the intervention and event onset.
 - b. An alternate etiology has been established.

7.4.2 Expectedness of SAEs

The Study PIs and Data Safety Monitoring Board (DSMB) will be responsible for determining whether an SAE is expected or unexpected. An adverse event will be considered unexpected if the nature, severity, or frequency of the event is not consistent with the risk information previously described for the intervention.

Table 10. Possible expected adverse events and grading scale.^a

CTCAE Term	Mild Grade 1	Moderate Grade 2	Severe Grade 3	Potentially Life Threatening Grade 4	Death Grade 5
Abdominal Pain (stomach ache)	Mild pain	Moderate pain; limiting instrumental ADL*	Severe pain; limiting self care ADL**	-	-
Allergic reaction	Systemic intervention not indicated	Oral intervention indicated	Bronchospasm; hospitalization indicated for clinical sequelae; intravenous intervention indicated	Life-threatening consequences; urgent intervention indicated	Death
Constipation	Occasional or intermittent symptoms; occasional use of stool softeners, laxatives, dietary modification, or enema	Persistent symptoms with regular use of laxatives or enemas; limiting instrumental ADL	Obstipation with manual evacuation indicated; limiting self care ADL	Life-threatening consequences; urgent intervention indicated	Death
Diarrhea (≥3 loose stools per day for 2 consecutive days)	Increase of <4 stools per day over baseline; mild increase in ostomy output compared to baseline	Increase of 4-6 stools per day over baseline; moderate ostomy output compared to baseline; limiting instrumental ADL	Increase of ≥7 stools per day over baseline; hospitalization indicated; severe increase in ostomy output compared to baseline; limiting self care ADL	Life-threatening consequences; urgent intervention indicated	Death
Dyspepsia (upset stomach or indigestion)	Mild symptoms; intervention not indicated	Moderate symptoms; medical intervention indicated	Severe symptoms; operative intervention indicated	-	-
Fever	38.0 - 39.0°C (100.4 - 102.2°F)	> 39 - 40.0°C (102.3 - 104.0°F)	> 40.0°C (>104.0°F) for ≤ 24 hours	> 40.0°C (>104.0°F) for > 24 hours	Death
Flatulence	Mild symptoms; intervention not indicated	Moderate; persistent; psychosocial sequelae	-	-	-
Lack/loss of appetite	Loss of appetite without alteration in eating habits	Oral intake altered without significant weight loss or malnutrition; oral nutritional supplements indicated	Associated with significant weight loss or malnutrition (e.g., inadequate oral caloric and/or fluid intake); tube feeding or TPN indicated	Life-threatening consequences; urgent intervention indicated	Death
Loose stools (not clinically defined diarrhea)	Mild symptoms; intervention not indicated	Moderate symptoms; limiting instrumental ADL	Severe symptoms; limiting self care ADL; hospitalization indicated	Life-threatening consequences; urgent intervention indicated	-
Nausea	Loss of appetite without alteration in eating habits	Oral intake decreased without significant weight loss, dehydration or malnutrition	Inadequate oral caloric or fluid intake; tube feeding, TPN, or hospitalization indicated	-	-
Rash (Cutaneous reaction)	Covering <10% body surface area (BSA) with or without symptoms (e.g., pruritus, burning, tightness)	Covering 10-30% BSA with or without symptoms; limiting instrumental ADL; rash covering >30% BSA with or without mild symptoms	Rash covering >30% BSA with moderate or severe symptoms; limiting self care ADL	-	-
Vomiting	Intervention not indicated	Outpatient IV hydration; medical intervention indicated	Tube feeding, TPN, or hospitalization indicated	Life-threatening consequences	Death

^a U.S. Department of Health and Human Services. Common Terminology Criteria for Adverse Events (CTCAE)

Version 5.0. Published: November 27, 2017.

Semi-colon (;) indicates 'or' within the description of the grade

Single dash (-) indicates grade is not available

Activities of Daily Living (ADL)

*Instrumental ADL refer to preparing meals, shopping for groceries or clothes, using the telephone, managing money, etc.

**Self care ADL refer to bathing, dressing and undressing, feeding self, using the toilet, taking medications, and not bedridden.

7.4.3 Severity of Event

Adverse events will be graded according to the National Cancer Institutes' Common Terminology Criteria for Adverse Events (CTCAE) v5.0:

1. Grade 1 Mild: asymptomatic or mild symptoms; clinical or diagnostic observations only; no intervention indicated; no to minimal impact on activities of daily living (ADL).
2. Grade 2 Moderate: minimal, local, or noninvasive intervention indicated; moderate impact on ADL.
3. Grade 3 Severe: severe or medically significant but not immediately life-threatening; hospitalization or prolongation of hospitalization indicated; disabling; needs major assistance with ADL.
4. Grade 4 Potentially life-threatening: life-threatening consequences; urgent intervention indicated.
5. Grade 5 Death: death related to AE.

Please note that a severe AE and an SAE are distinct terms.

7.5 Expected Risks

The expected risks and side effects (listed in **Table 10**) for each intervention and procedure are as follows:

- Cultured yogurt: digestive/gastrointestinal problems such as stomach ache, constipation, diarrhea, flatulence, fever, lack of appetite, vomiting, and loose, watery bowels, and allergic reaction to any of the yogurt ingredients, most likely strawberry.
- Amoxicillin-clavulanate: nausea and/or vomiting, diarrhea, upset stomach and mild to severe skin rash. The most serious potential risk is diarrhea caused by a *Clostridium difficile* infection. Symptoms of *C. difficile* infection include stomach pain or tenderness, bloody stools, fever, nausea, and diarrhea.
- Fecal sample collection: there are no known risks. However, there may be some discomfort with fecal sample collection.

These risks are considered to be minimal and are addressed in the protocol and consent form.

It will be explained to the participants that there may also be side effects, other than those listed, that we cannot predict. Many side effects go away shortly after the treatments are stopped, but in some cases side effects can be serious, long lasting or permanent. Participants will be informed to discuss any questions about potential risks with the researchers and their primary care providers. Anyone who develops evidence of allergy or hypersensitivity to any component of the yogurt products will be withdrawn from the study and receive no further doses. We will continue to monitor these participants for safety until the event sufficiently resolves.

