5.3 Concomitant Interventions

5.3.1 Allowed Interventions

Once enrolled, participants are allowed interventions or medications as needed, at the guidance of their

personal physician. Since the use of additional or concomitant interventions could bias results, participants will be asked to report any of these additional treatments. Participants will be advised multiple times before enrollment to avoid concomitants, but once enrolled they will be told of the importance of articulating usage. All participants will be given a list of products they should avoid during the study. Due to the intention-to-treat principle, participants will not be removed from the study but will continue with all planned study interventions and data collection.

If the participant takes any antibiotics within the 30-day run-in period, they will repeat another 30-day run-in upon completion of the antibiotics, prior to initiation of the interventions.

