5.3.3 Prohibited Interventions

Participants will be *ineligible* if they are taking the following medications at the time of enrollment:

- Daily diabetes or asthma medication
- Any gastrointestinal medications, i.e. medicines for irritable bowel syndrome, gastroesophageal reflux disease, inflammatory bowel disease, etc. (a full medication list will be reviewed by the PI prior to enrollment).

Participants must also avoid the following for the duration of the study:

- Any probiotic not provided by the study.
- Any antibiotic not provided by the study.

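### The antibiotic carries the risk the plan calls most serious, but the mandatory dose-stops are triggered only by the yogurt, and Section 5.3.1 cites intention-to-treat as a reason to keep dosing

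*Combined protocol and SAP*

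**What the plan says.** Section 7.5 of the combined protocol and SAP lists the expected risks by intervention. For AMC it states: "The most serious potential risk is diarrhea caused by a *Clostridium difficile* infection". It names blood in the stool and fever among the symptoms, and it includes skin rash up to severe as an AMC risk.

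Three rules oblige staff to stop an individual's dosing:

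- Section 7.1: a participant with "evidence of allergy or hypersensitivity to any component of the investigational product will be withdrawn from the clinical study".
- Section 7.5: a participant with allergy or "hypersensitivity to any component of the yogurt products will be withdrawn from the study and receive no further doses".
- Section 6.7.2, for a wrong bin number: "the participant should be alerted not consume any more drinks until further notice".

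Section 8 adds permissive grounds. Individuals may be withdrawn for adverse events, which the clinical PI will discuss with them. They may also be withdrawn for related serious events as judged by the PIs, the participant or the participant's physician.

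On contact, Section 6.7.1 says "Follow-up phone visits will be completed on Days 7, 14 and 30", each with a window of two days either side. AMC is taken twice daily on days 1 to 7 (5.1), and there is no clinic visit (6.5.1).

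On other treatment, Section 5.3.1 says that once enrolled, "participants are allowed interventions or medications as needed, at the guidance of their" personal physician. It then says: "Due to the intention-to-treat principle, participants will not be removed from the study but will continue with all planned study interventions". Section 5.3.3 tells participants to avoid, for the whole study, "Any antibiotic not provided by the study".

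**The concern.** The study gives an antibiotic to people who are not being treated for an infection. If one of them develops suspected C. difficile diarrhea or a drug rash, further AMC has no benefit to set against the harm. One would expect a rule saying which symptoms end AMC and whom to call. The mandatory rules deal with the yogurt instead, and the hypersensitivity stop in 7.5 leaves out AMC although the same section lists rash as an AMC risk.

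Two features add to this. The first planned contact normally comes when the course is ending. And 5.3.1 turns intention-to-treat into a dosing instruction. That principle says participants are analyzed in the group to which they were randomized, whatever they took. It gives no reason to keep anyone on a drug. Staff reading the sentence at face value could take it as a reason to continue AMC in someone already receiving other treatment.

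**Working it through.** The main point is a comparison of rules and a count of days. No sample size or power figure has to be reproduced for it.

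**1. What triggers each stop during dosing**

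- 7.1: allergy to the investigational product. Mandatory. Trigger: yogurt.
- 7.5: allergy to the yogurt products. Mandatory. Trigger: yogurt.
- 6.7.2: wrong bin number. Mandatory. Trigger: yogurt.
- 8: adverse event, after discussion with the clinical PI. Permissive. Any cause, no grade or symptom named.
- 8: related serious adverse event. Permissive. Any intervention.

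No mandatory trigger is diarrhea, suspected C. difficile or a reaction to AMC. Withdrawal for yogurt allergy would presumably end AMC too, but the trigger remains the yogurt. Table 10 already grades diarrhea, so a threshold could be stated without new definitions.

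**2. Doses that a scheduled call can still save**

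The course is 2 × 7 = 14 doses. Assuming both doses on the day of contact are taken, the doses left after contact on day k are max(0, 2 × (7 − k)):

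| Contact day | 3 | 4 | 5 | 6 | 7 | 8 | 9 |
|---|---|---|---|---|---|---|---|
| Doses left | 8 | 6 | 4 | 2 | 0 | 0 | 0 |

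If the contact comes before that day's doses, up to two more can be saved on days 3 to 7. The planned window is days 5 to 9. Before it, staff learn of an event only if the participant reports it. The diary lists the Table 10 events, and Table 10 has no item for blood in the stool, so that symptom would have to be written in as an unlisted event.

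**3. Sections 5.3.1, 5.3.3 and 8 together**

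Section 5.3.1 permits physician-guided medication, then says users continue the interventions. Section 5.3.3 excludes non-study antibiotics and makes no exception for medical need. Section 8 permits withdrawal for adverse events. Nothing says which takes precedence.

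**4. Context only: how many people might be affected**

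- Diarrhea at the plan's 15% (3.2): 60 × 0.15 = 9. At the rate in the earlier adult study (Table 1: 2/21 and 2/19, together 4/40 = 10%): 60 × 0.10 = 6.
- C. difficile at the background share of 10-20% of diarrhea (2.7): 9 × 0.10 = 0.9 to 9 × 0.20 = 1.8 cases. The chance of at least one is 1 − (1 − 0.015)^60 = 0.60 to 1 − (1 − 0.03)^60 = 0.84.
- At an assumed share of 1%: 0.09 cases, and 1 − (1 − 0.0015)^60 = 0.09.

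The background share probably overstates the risk in healthy adults, and the 1% has no source in the documents. Onset times are not given, so the number of avoidable doses is unknown.

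**5. Context only: would stopping AMC dilute the acetate contrast?**

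From 9.2: baseline 45, SD 18 after antibiotic, falls of 42% and 15%. Control mean = 45 × 0.58 = 26.1; BB-12 mean = 45 × 0.85 = 38.25; difference 12.15; d = 12.15 / 18 = 0.675. This is a derived value, consistent with the plan's expectation of more than 0.6 (9.1).

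Let shares pc (control) and pt (BB-12) stop and recover a fraction r of the acetate fall, with the SD unchanged. Then difference = 12.15 − pc × r × 18.9 + pt × r × 6.75.

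- Three stop, controls at twice the BB-12 rate (pc 0.075, pt 0.0375): d = 0.64 at r = 0.5 and 0.61 at r = 1.
- Nine stop, equal rates (0.15 each): d = 0.62 and 0.57.
- Nine stop, controls at twice the rate (pc 0.225, pt 0.1125): d = 0.58 and 0.48.

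The stop rates and r are assumptions.

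**The case against.** The strongest reply is that AMC can be stopped under the plan as written. Section 8 sets no minimum grade for adverse events, commits the clinical PI to discussing them, and lets the participant or treating physician judge a related serious event. Section 10.2.3 lists a Withdrawal from Intervention form and a Diarrhea Report and Follow-up form. Missed interventions alone do not lead to withdrawal (5.4, 8), so a volunteer can stop AMC and stay in the study. Adverse events may be reported spontaneously (7.2), a 24-hour line exists (7.1, written for allergic or idiosyncratic reactions), and 5.1 points to the AMC package insert. In the earlier study of 40 adults on 10-day penicillin-class courses (2.10) there were no serious adverse events and no withdrawals for adverse events. Consent text, the Diarrhea Report form and the insert are not shown, and any of them may tell participants when to stop or call.

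All of this stands. It shows that stopping is possible and that events may be detected early. It does not supply a symptom or grade at which AMC must stop. The choice of grade is a clinical one, and leaving some room for PI judgment is legitimate.

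A reader might infer more than the documents support:

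- *That the plan orders dosing through diarrhea, or forbids stopping AMC.* It does not. Section 8 applies, and the entry in 5.1 that modifications are not applicable may only mean a fixed dose.
- *That C. difficile treatment is barred.* Section 5.3.1 allows medication on a physician's advice. The difficulty is that 5.3.3 makes no matching exception.
- *That an event on the day of the first call goes unattended until the next one.* The sentence in 6.7.1 defines the recall period of the Follow-Up Form. Section 6.7.2 separately requires an adverse event form at once and immediate alerts for serious events.

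**Conclusion.** The concern holds as a gap in participant safety. AMC carries the risk that the plan itself ranks as most serious, yet no mandatory individual stop is triggered by an AMC event. The scheduled call can save at most 4 of 14 doses if made on day 5, and none from day 7 on, counting from the day after the call. Timely stopping thus rests on unprompted reporting followed by a case-by-case decision. The use of intention-to-treat in 5.3.1 is an error whatever the incidence of C. difficile.

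The day count rests only on the dosing and call schedule. The case numbers and the effect on d rest on assumptions and are context: about 6 to 9 participants with diarrhea, and a chance of at least one C. difficile case anywhere from 9% to 84% at the 15% diarrhea rate. They do not show that harm is likely, and the finding does not depend on them. The gap does not threaten the acetate conclusion. Material not shown may close part of it. The rules in the protocol should still be corrected, because they are what staff work from.

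**What to change.** - **5.3.1:** say that participants stay in follow-up and in the intention-to-treat analysis whether or not dosing continues, and that safety decisions under Section 8 take precedence.
- **5.3.3:** except antibiotics that are medically needed.
- **7.1 and 7.5:** extend the hypersensitivity stop to AMC.
- **Section 8:** state that bloody stools, fever with diarrhea, or diarrhea at or above a grade set by the clinical PI (for example Grade 2 in Table 10) means stop AMC, call the study line the same day and be referred for assessment. Milder diarrhea without these signs can continue under PI judgment.
- **Contact and diary:** add one call or text on day 3 or 4, when 8 or 6 doses are still to come, and a bloody-stool item in the diary. Record the last AMC dose date, and keep those who stop in the day-7 intention-to-treat analysis.

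The cost is a few reworded sentences, one diary item and 60 short contacts, with no added visit. Because 6.3 says no study party is responsible for further medical care, the sponsor should state who pays for assessment. The scientific downside is less antibiotic exposure in those who stop. With three stops the derived d stays above the 0.6 milestone under the assumptions shown. With nine it could fall below, which is a reason not to stop AMC for every mild case.
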